Subject Enrollment																				
Follow up studies																				
Longitudinal follow up																				
Reports for DSMB																				
Statistical Analysis																				
Interpretation of Results																				
Progress Reports																				
Dissemination of results																				

B. Specific Aims

Specific Aim 1: To determine the short and long term effects of ZA on BMD values of the hip, distal femur and proximal tibia in patients with acute SCI relative to patients receiving placebo.

Primary hypothesis: Subjects treated with ZA will have at least a 50% smaller percentage decline in BMD values for the hip, distal femur and proximal tibia at 4 and 12 months post-injury than control subjects.

Secondary hypothesis 1: Subjects treated with ZA will maintain original BMD values for the hip, distal femur and proximal tibia at 4 months and lose no more than 5% at 12 months post-injury than control subjects.

Secondary hypothesis 2 (Exploratory): Incidence of fractures in the hip, distal femur, and proximal tibia will be at least 50% lower in subjects treated with ZA compared to controls. This final hypothesis is exploratory, since we do not expect to have the numbers to achieve statistical significance given the relatively low frequency of sub-lesional fractures in SCI.

Specific Aim 2: To measure and compare selected blood biomarker levels: 1) pro-osteoclastogenic factor IL-1 β ; 2) bone formation marker P1NP; and 3) bone resorption marker serum C terminal telopeptide of type I collagen (s-CTX) in subjects treated with ZA to control subjects.

Primary hypothesis: Subjects treated with ZA will have lower levels of serum marker of bone resorption s-CTX at 4 and 12 months, relative to controls. *In terms of absolute marker levels*, we hypothesize that the ZA subjects will have s-CTX values within the reference range at 4 and 12 months, in contrast to control subjects whose resorption marker levels will be significantly above the reference range at all of the time points.

Secondary hypothesis: Levels of serum marker of bone formation P1NP will not be lower than control subjects at 4 and 12 months.

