Challenges exist to giving oral alendronate in the setting immediately following SCI. Limitations to upright posture include post-operative spinal stability precautions, delay in brace fitting needed to maintain stability in sitting position, autonomic effects of orthostasis, and pain. Erosive esophagitis may occur following consumption of oral bisphosphonates, unless patients are able to sit fully upright after administration of medications. In the previously described study by Gilchrist⁵⁶, authors specifically reported no difficulties encountered with GI symptoms. This may have been due to the number of subjects with AIS Grades B-D or with thoracolumbar neurological levels of injury. Severe orthostatic hypotension is less common in these groups, permitting earlier functional mobility and facilitating upright positioning sooner after injury. Because IV formulations can be administered in the supine position, investigators have explored the use of IV bisphosphonates in the setting of acute SCI. An early investigation by Nance⁵⁷ examined the use of IV pamidronate, a relatively weak bisphosphonate, within 6 weeks of injury in 24 subjects with traumatic SCI. This non-randomized trial divided the sample into 14 subjects receiving 30 mg of IV pamidronate monthly for 6 consecutive months and 10 controls with comparable degrees of SCI given standard rehabilitation therapy but no drug. Interpretation of results was limited by the heterogeneity of subjects: some had sensory and motor complete injuries (AIS A), while others were AIS D, a subset of whom were ambulatory. Outcomes at 12 months evaluated BMD at the hip, distal femur and proximal tibia by percent change from baseline. Only the pamidronate-treated AIS D subjects demonstrated an increase in BMD and this rise was observed only in the distal femur. The proximal tibia and hip were largely unchanged from subjects' baseline BMD, but control subjects demonstrated BMD losses of .5%, 13.4% and 10.5% respectively. In this study, control subjects with AIS grade A injury lost 14.6% of original BMD, while pamidronate-treated subjects lost only 6.5% of their original BMD. Neither group was able to maintain their pre-injury bone density. A second investigation by Bauman⁵⁸ examined the effect of IV pamidronate on sublesional osteoporosis in 11 subjects with acute SCI 22-65 days post injury. Although early mild reduction in the degree of BMD loss was observed, by the end of 12 months both placebo and pamidronate-treated subjects lost statistically similar amounts of BMD below the level of injury: 18 vs. 15% in the pelvis; 28 vs. 17% in the distal femur, and 42 vs. 36% in the proximal tibia.

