The sample size calculation is based on the primary outcome of BMD loss at the proximal tibia at 12 months. A set target of at least 50% reduction in percent BMD loss between treatment and control groups is projected. Expected BMD loss is taken from the placebo group of Bauman⁽⁵⁸⁾.

Subjects in this study lost 8% +/- 3% BMD at 3 months and **29% +/- 13%** at 12 months in the proximal tibia. The effect size (difference in mean percent reduction divided by standard deviation) for a 50% reduction in BMD loss is 1.3 at 3 months and 1.1 at 12 months. Assuming 2:1 randomization, two-sample t-test, 80% power and two-sided type-I error rate of 5%, we would need a total sample size of 24 for an effect size of 1.3, 33 for an effect size of 1.1, and 39 for an effect size of 1.0. We plan to enroll 48 subjects to allow for potential attrition. With a dropout rate of 18% we would reach a final sample of 39; a dropout rate of 30% would result in a final sample of 33. The enrollment of 10 subjects/year (total = 40) would still allow an 18% drop out to achieve a final sample of 33.

2. Randomization Method

The randomization schedule will be generated by the TJU Division of Biostatistics. Randomization will use the method of random permuted blocks. The block size will not be disclosed to the investigators. The TJU Division of Biostatistics will prepare a randomization scheme document to be kept by the TJUH Investigational Drug Service (IDS). Once a subject is confirmed to be eligible and the informed consent is completed, the IDS will be alerted to assign a randomization and prepare for the subsequent medication preparation and delivery. A completed randomization assignment log will be returned to Biostatistics so they can monitor randomization and accrual.

3. Management of Study Drug Infusion

The TJUH Investigational Drug Service is a well-established service within the Pharmacy Department that participates in numerous inpatient and outpatient research protocols. The IDS reviews all inpatient investigational drug protocols and assists with patient enrollment (randomization), staff education and maintenance of study records, including protocol budgets. The IDS maintains all investigational drug records in accordance with FDA regulations as well as with the policies and procedures of the Institutional Review Board. The IDS provides the procurement, storage, dispensing and maintenance of records for all investigational drugs.

4. Study Activities and Assessments

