We will compare the treatment and control groups for baseline characteristics using t-tests and Chi-square tests as appropriate. Specifically, we will compare age at injury, baseline FRAX fracture risk, sex and injury level (tetraplegia/paraplegia) distribution. The level of significance for all analyses will be 0.05.

2. Evaluation of Hypotheses

Specific Aim 1: To determine the short and long term effects of zoledronic acid on BMD values of the hip, distal femur, and proximal tibia in patients with acute SCI relative to patients receiving placebo.

The primary hypothesis is that subjects treated with zoledronic acid will have at least a 50% smaller percentage decline in BMD values for the hip, distal femur and proximal tibia at 4 and 12 months post-injury than control subjects.

Analysis: For each of the bone sites to be evaluated, a percent change from baseline ([baseline BMD – follow-up BMD]/baseline BMD) will be modeled using mixed effects linear regression. Fixed effects will be included for treatment assignment, time, treatment by time interaction, and baseline BMD level. A random intercept term will be included to account for correlation among repeated measurements from the same subject. Within this regression model, we will estimate the difference between treatment groups at 4 and 12 months and test for significance of this difference. If the outcome of percent change is not normally distributed, we will apply an appropriate transformation (e.g., log, logit). If the necessary transformation is too complex for interpretation, we will consider using rank-based methods.

Secondary hypothesis 1 is that subjects treated with zoledronic acid will maintain original BMD values for the hip, distal femur and proximal tibia at 4 months and lose no more than 5% at 12 months post-injury.

Analysis: We will estimate the mean percent change at 4 and 12 months for the active treatment group along with associated 95% confidence intervals from the results of the mixed effects regression. BMD values at 4 months will be considered equivalent to those at baseline if the bounds of the confidence interval are within +/-2%. At 12 months, we will test the one-sided null hypothesis that the percentage decline is greater than 5% vs. the alternative that it is less than or equal to 5%.

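### One endpoint is powered but six comparisons are called primary, each tested at 0.05, and no rule says which results make the trial positive

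*Combined protocol and SAP*

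**What the plan says.** The sample-size text (Section D.3, item 1) is explicit: "The sample size calculation is based on the primary outcome of BMD loss at the proximal tibia at 12 months". The calculation is for one test: "Assuming 2:1 randomization, two-sample t-test, 80% power and two-sided type-I error rate of 5"%. It gives totals of 24, 33 and 39 for effect sizes 1.3, 1.1 and 1.0, and plans 48 enrolled so that 39 remain after 18% dropout or 33 after 30%.

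Other sections define the primary question more widely:

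- **Section A, Primary Outcome:** BMD change by DXA at 4 and 12 months, compared at all three sites.
- **Section B, Aim 1:** the primary hypothesis reads "Subjects treated with ZA will have at least a 50% smaller percentage decline in BMD values for the hip, distal femur and proximal tibia", and it covers both visits.
- **Section E.2, Aim 1:** the same hypothesis, covering "BMD values for the hip, distal femur and proximal tibia at 4 and 12 months post-injury than control subjects". A separate mixed model is fitted for each site, and within it "we will estimate the difference between treatment groups at 4 and 12 months and test for significance of this difference".
- **Section E.1:** "The level of significance for all analyses will be 0.05".

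Neither the protocol sections nor the analysis section gives a testing order, a multiplicity adjustment, or a statement that one, some or all of the comparisons must be significant.

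**The concern.** Three sites at two visits make six primary tests. Six is a minimum, because the hip subregion is not named. Three decision rules are open: the single test of Section D.3; all six, which the conjunctions in the hypothesis suggest; or any one of six, which is furthest from the wording but not excluded. They differ in type I error and in power. A result significant at some comparisons and not at others could be called positive or negative by a rule chosen after the data are seen. The 5% and 80% in Section D.3 were computed for the first rule only.

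**Working it through.** **Inputs from the plan (Section D.3).** Proximal tibia placebo loss is 8% (SD 3) at 3 months and 29% (SD 13) at 12 months. A halved loss gives effect sizes 4/3 = 1.33 and 14.5/13 = 1.12, stated as 1.3 and 1.1. The test is a two-sample t-test, two-sided 5%, 2:1 allocation.

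**Assumed.** Correlations between sites and visits (0 to 0.9), hip and femur effect sizes, and the 3-month effect applied at month 4. The documents give no correlations and no SD for hip or femur. The planned baseline-adjusted mixed model may give somewhat different power from the t-test.

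**1. Reproducing the plan's figures.** Power comes from the noncentral t with noncentrality d/√(1/n₁+1/n₂) and N−2 degrees of freedom.

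- N = 24 (16:8), d = 1.3: power 0.818
- N = 33 (22:11), d = 1.1: 1.1/√(1/22+1/11) = 2.979, critical t 2.040, power 0.823
- N = 39 (26:13), d = 1.0: power 0.818

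The totals 24, 33 and 39 reproduce, as does the attrition: 48 × 0.82 = 39.4 and 48 × 0.70 = 33.6.

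**2. Rule A, proximal tibia at 12 months only.** At d = 1.1, power is 0.823 at N = 33, 0.884 at N = 39 and 0.940 at N = 48, with error 5%.

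**3. Rule B, all six significant.** With one true null and five large effects, simulated error is 0.051 two-sided (nominal 0.05), so no adjustment is needed. For power, suppose the tibia effects hold at every site. Under independence, N = 33 gives 0.926³ × 0.823³ = 0.44 and N = 39 gives 0.961³ × 0.884³ = 0.61. Simulation over correlations (site/visit):

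| Correlation | N = 33 | N = 39 | N = 48 |
|---|---|---|---|
| 0/0 | 0.44 | 0.61 | 0.79 |
| 0.3/0.3 | 0.51 | 0.66 | 0.82 |
| 0.7/0.6 | 0.64 | 0.75 | 0.87 |
| 0.9/0.9 | 0.74 | 0.82 | 0.90 |

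Illustrations with smaller hip and femur effects, over correlations 0 to 0.9:

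| Hip and femur effects | N = 33 | N = 39 |
|---|---|---|
| 0.9 at both | 0.14–0.52 | 0.25–0.61 |
| 0.8 at both | 0.08–0.40 | 0.14–0.48 |
| Section C losses halved, SD 13 assumed | 0.24–0.44 | 0.35–0.51 |

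The last row takes the 12-month losses that Section C quotes, with pelvis standing in for hip: 9/13 = 0.69 and 14/13 = 1.08, the tibia at 14.5/13 = 1.12, and 1.3 at month 4 for every site.

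**4. Rule C, any one of six.** Under independence, error is 1 − 0.95⁶ = 0.265. Simulation at 26:13 under the null:

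| Correlation | Two-sided | Favouring ZA |
|---|---|---|
| 0/0 | 0.264 | 0.140 |
| 0.5/0.5 | 0.222 | 0.111 |
| 0.7/0.6 | 0.191 | 0.096 |
| 0.9/0.9 | 0.117 | 0.058 |

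The benchmarks for a single test are 0.05 and 0.025.

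**5. The input behind Rule A.** Section D.3 says "Expected BMD loss is taken from the placebo group of" the cited pamidronate study (reference 58) and uses 29%. Section C reports 12-month losses from that study as "18 vs. 15% in the pelvis; 28 vs. 17% in the distal femur, and 42 vs. 36% in the proximal tibia", placebo named first. At N = 33, 80% power needs an effect size of 1.068. A halved loss therefore keeps 80% only if the SD is at most 14.5/1.068 = 13.6 points (29% loss), 18/1.068 = 16.9 (36%) or 21/1.068 = 19.7 (42%). With the SD held at 13, power would be 0.95 or 0.99 for a 36% or 42% loss. If the SD scales with the mean, it stays 0.83.

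**The case against.** Type I error is at or below 5% under both readings that the text supports: the endpoint named in Section D.3, and the conjunctive hypothesis. Inflation needs the any-one rule, which nothing in the wording suggests. This is fair, and the 12% to 26% should be read as what an unstated rule permits, not as what the plan intends.

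The low all-six figures also lean on assumptions. Effects of 0.9 and 0.8 have no source in the documents. Holding the SD at 13 for a smaller hip loss is unfavourable, since the two mean and SD pairs in Section D.3 (ratios 0.375 and 0.45) show the SD rising with the mean. If the SD scales at 0.45, 12-month effects are about 1.1 everywhere and all-six power is 0.47–0.75 at N = 33 and 0.64–0.83 at N = 39. Zero correlation within a person is unrealistic; at 0.5 to 0.9 with tibia effects, power is 0.58–0.74 and 0.70–0.82. The mixed model may also keep month-4 data from subjects lost later, and with all 48 evaluable the all-six rule reaches 0.79–0.90.

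These points narrow the range and make the smaller-effect cases illustrations only. They do not supply a rule, and even the favourable settings stay mostly below 80% at the 33 to 39 evaluable subjects planned for. Finally, a tibia-only primary demotes the hip and femur, although Section A states the aim as reducing loss at hip and knee. That is a real cost, and the choice belongs to the sponsor.

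**Conclusion.** The concern holds and should be fixed before unblinding. The contradiction between Section D.3 and Sections A, B and E is in the text and needs no assumption. The stated 5% and 80% hold together if the 12-month proximal tibia test alone decides, given the 29% mean and SD of 13. Under an all-six rule, power was never computed, and it reaches 80% at the planned evaluable numbers only in the best case examined: 39 subjects, tibia-sized effects everywhere and correlations near 0.9. Under an any-one rule, error is roughly two to five times the nominal 5%. The sizes for the last two rules rest on assumed correlations and on assumed hip and femur effects.

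**What to change.** State one decision rule before unblinding. The option that keeps the existing sample size and its power is:

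1. Name ZA versus placebo in percent BMD change at the proximal tibia at 12 months as the single primary test, two-sided 0.05, as Section D.3 already does.
2. Bring the Primary Outcome in Section A and the Aim 1 primary hypothesis in Sections B and E.2 into line with it.
3. Make the other five comparisons secondary, in a prespecified fixed order of the sponsor's choosing or under Holm.
4. Limit the Section E.1 sentence on the 0.05 level to match.
5. Reconcile the 29% ± 13% in Section D.3 with the proximal tibia figures in Section C, because the single primary rests wholly on that input.

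An explicit all-six rule or a full hierarchy would also remove the ambiguity, but an all-six rule needs its own power calculation with hip and femur means and SDs.

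The cost is wording in three sections and one check of a cited figure. Five comparisons lose primary status. No new data are needed and planned enrolment stays at 48.

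### The Aim 1 mixed model uses one variance for both arms and both visits; the 12-month ZA-placebo interval is too narrow, more so if ZA reduces the spread of loss, and the 4-month ZA-only interval is too wide

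*Combined protocol and SAP*

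**What the plan says.** Section E.2, Specific Aim 1, models percent change in BMD at each site by mixed effects linear regression: "Fixed effects will be included for treatment assignment, time, treatment by time interaction, and baseline BMD level". A random intercept handles the repeated measurements. The text does not mention residual variance by arm or by visit, so a common variance is the default reading rather than an explicit choice. The ZA-placebo differences at 4 and 12 months come from this model. So do the ZA-only results for secondary hypothesis 1: "We will estimate the mean percent change at 4 and 12 months for the active treatment group along with associated 95% confidence intervals". Those feed the ±2% equivalence criterion at 4 months and the one-sided 5% test at 12 months. The only fallback, a transformation or ranks, is triggered by non-normality and not by unequal variance.

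Section D.3, Sample Size Calculations, supplies the only planning SDs: "Subjects in this study lost 8% +/- 3% BMD at 3 months and 29% +/- 13% at 12 months in the proximal tibia". Their origin is stated: "Expected BMD loss is taken from the placebo group of Bauman". The target is proportional: "A set target of at least 50% reduction in percent BMD loss between treatment and control groups is projected". Section D fixes allocation at 2:1, ZA to placebo.

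**The concern.** A random intercept plus one residual variance forces the same total variance on every arm and visit. Two features of this trial strain that.

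- **Visits.** The plan's own SDs differ more than fourfold between 3 and 12 months (13/3 = 4.3).
- **Arms.** The primary hypothesis is a 50% smaller percentage decline. If that came about by halving each patient's loss, the ZA SD would halve too, from 13 to 6.5 at 12 months. With 2:1 allocation the more variable arm would then be the smaller one, which is the direction in which a pooled standard error understates the uncertainty of a difference.

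At stake are the error bars on the main 12-month result and both ZA-only conclusions of secondary hypothesis 1. Correcting the visits alone would leave the arm problem in place.

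**Working it through.** **Inputs.** Section D.3: placebo loss 8% (SD 3) at 3 months and 29% (SD 13) at 12 months; 39 completers after 18% dropout, hence 26 ZA and 13 placebo at 2:1.

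**Assumptions.** The 3-month SD stands in for 4 months. The ZA SD is r times the placebo SD at each visit; 12-month values of 13, 9.75, 6.5 and 5 are shown (r = 1, 0.75, 0.5, 0.38). Within-subject correlation is 0.5. There is no baseline covariate and no missing visit.

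**The plan's own figures.** Effect sizes: 4/3 = 1.33 and 14.5/13 = 1.12, agreeing with 1.3 and 1.1. An equal-variance t-test at 2:1, two-sided 5%, needs 24, 33 and 39 patients for effects of 1.3, 1.1 and 1.0, with power 81.8%, 82.3% and 81.8%. The sample sizes reproduce, and they rest on a single SD.

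**Standard errors at r = 0.5.**
- True SE of the 12-month difference: √(6.5²/26 + 13²/13) = √(1.625 + 13) = 3.82.
- Arms pooled, visits separate: pooled SD = √((25×42.25 + 12×169)/37) = 9.13; SE = 9.13×√(1/26 + 1/13) = 3.10. Ratio to true: 0.81.
- As written, with complete data, the model's variance is the average of the two visit variances after pooling over arms. At 4 months: (25×2.25 + 12×9)/37 = 4.44. At 12 months: 83.36. Average 43.90, SD 6.63; SE = 6.63×√(1/26 + 1/13) = 2.25. Ratio to true: 0.59.

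**With equal arm SDs (r = 1).** True SE = 13×√(1/26 + 1/13) = 4.42. As written: √((9 + 169)/2) = 9.43, SE 3.20, ratio 0.73. This part needs no assumption about a smaller ZA SD.

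**Simulated coverage of the nominal 95% interval for the 12-month difference, 26:13.**

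| ZA SD at 12 months | As written | Visits separate, arms pooled | Separate by arm and visit |
|---|---|---|---|
| 13 | 85% | 95% | 95% |
| 9.75 | 81% | 93% | 95% |
| 6.5 | 75% | 89% | 95% |
| 5 | 73% | 87% | 95% |

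A check with 150 REML fits at r = 0.5 gave a model SE of 2.27 against an empirical 4.11.

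**ZA-only, 4 months, r = 0.5.** As written, SE = 6.63/√26 = 1.30, half-width about 2.6 points. The true SE is 1.5/√26 = 0.29, half-width about 0.6. An interval of ±2.6 cannot fit inside ±2, whatever the true change.

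**ZA-only, 12 months.** As written, the SE is 1.30 against a true 6.5/√26 = 1.27, so the two errors nearly cancel. The model variance equals the true ZA variance when 89×(25r² + 12)/37 = 169r², that is r² = 0.265 and r about 0.52. Above that, the interval is too narrow. The one-sided 5% test has a simulated level of about 5% at SD 6.5, 9% at 9.75 and 11% at 13. If visits are separated but arms stay pooled, the cancellation is lost: the SE becomes 9.13/√26 = 1.79, and the level at SD 6.5 falls to about 1.3%.

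**Power.** With variances separate by arm and visit and 39 completers, power for a 14.5-point difference is 88.2% at ZA SD 13 and about 94% at 6.5.

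**The case against.** The strongest objection is that the smaller ZA SD is not in the documents. The two SDs in section D.3 describe one external placebo group at two times. They show spread growing over time, with time and mean loss fully confounded, and neither concerns a treated arm. A reader might infer that the plan's own figures prove the ZA arm less variable; they do not. The source study had 11 subjects in all (section C, on early bisphosphonate studies). If 5 or 6 were on placebo (an assumption), the 95% interval for an SD of 13 runs from about 8 to 32 or 37, too vague to establish a variance law. This objection stands. The ZA SD is therefore an assumed range, and at equal SDs arm pooling does no harm.

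A reader might also infer that borrowing the placebo spread makes the ZA-only tests uniformly conservative. For the model as written this is wrong at 12 months: the level is about right at half SD and too high above it. The conservative result appears only in a half-corrected model.

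Nor does arm pooling threaten the null. If SD follows mean loss, arms with no effect share one distribution, and arm pooling does not inflate type I error. Visit pooling is different: as written, with equal SDs, the 12-month between-arm test has type I error of about 15%.

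What the objection does not remove is the visit fault, which rests on the documented SDs, or the plausibility of unequal arms under a proportional target.

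**Conclusion.** The point holds in a limited form. As written, the Aim 1 model gives the 12-month ZA-placebo difference an interval covering about 73% to 85% instead of 95% over the assumed ZA SDs of 5 to 13. Visit pooling is the larger share. Arm pooling alone takes coverage from 95% (equal SDs) to about 87% (ZA SD 5), and it bears on intervals under a real effect. The 4-month ZA-only interval is much too wide: 4.4 times at half SD (1.30/0.29) and 3.1 times even with equal SDs. The 12-month ZA-only test can err in either direction, depending on an SD that the plan does not give. The documents do not support a claim of lost power for the primary comparison.

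All figures are for the proximal tibia, the only site with planning SDs. The baseline covariate would change the exact values.

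**What to change.** In section E.2, Specific Aim 1, prespecify an unstructured covariance over the two visits with variances that differ by arm, and Satterthwaite or Kenward-Roger degrees of freedom. State that the treatment contrasts, the ±2% interval and the 5% test all come from that model. At a single visit this amounts to the Welch comparison. Make both changes together, because separating the visits alone leaves about 89% coverage and a 1.3% test level at ZA SD 6.5.

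The cost is one clause and some effective degrees of freedom. If the SDs are in fact equal, power falls from 89.2% to 88.2% with 39 completers and from 83.3% to about 81.8% with 33, still above the planned 80%. If the ZA SD is half the placebo SD, the honest 12-month interval is about ±8.1 points rather than ±4.6. No extra patients or measurements are needed.

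### Aim 1's random-intercept model implies one variance at months 4 and 12, so the 12-month proximal-tibia test has about 7-16% type I error if the month-4 SD is 11% down to 3%

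*Combined protocol and SAP*

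**What the plan says.** Section E.2, Specific Aim 1, models percent change from baseline separately for each bone site by mixed-effects linear regression. The fixed effects are treatment, time, their interaction and baseline BMD. The covariance is described in one sentence: "A random intercept term will be included to account for correlation among repeated measurements from the same subject". Both visit-specific comparisons come from this model: "Within this regression model, we will estimate the difference between treatment groups at 4 and 12 months and test for significance of this difference". No residual structure, visit-specific variance, robust standard error or degrees-of-freedom method is given.

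There is one fallback. "If the outcome of percent change is not normally distributed, we will apply an appropriate transformation (e.g., log, logit"), and if the result is too hard to interpret, "we will consider using rank-based methods". The plan does not say how normality is to be checked.

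Secondary hypothesis 1 uses the same model twice. At month 4: "BMD values at 4 months will be considered equivalent to those at baseline if the bounds of the confidence interval are within +/-2" percent. At month 12: "At 12 months, we will test the one-sided null hypothesis that the percentage decline is greater than 5" percent.

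Section D.3, Sample Size Calculations, names the key comparison: "The sample size calculation is based on the primary outcome of BMD loss at the proximal tibia at 12 months". It takes its inputs from the placebo group of a small pamidronate study (11 subjects in all, according to section C): loss of 8% with SD 3% at 3 months, and 29% with SD 13% at 12 months.

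**The concern.** A random intercept plus one residual variance makes the total variance equal at the two visits. Bone loss after injury accumulates, and the plan's own SDs rise about fourfold between months 3 and 12. If the month-4 SD is smaller than the 12-month SD, pooling makes the 12-month standard error too small and the month-4 standard error too large. The 12-month proximal-tibia test would then reject too often under the null. Month 4 would lose power, and the interval used for the +/-2% rule would be too wide.

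**Working it through.** **The plan's own sample sizes.** Effect sizes are (8/2)/3 = 1.33 and (29/2)/13 = 1.12, which the plan rounds to 1.3 and 1.1. An exact noncentral-t calculation (2:1, two-sided 5%) gives 81.8%, 82.3% and 81.8% power at N = 24, 33 and 39 for effect sizes 1.3, 1.1 and 1.0. The stated sizes reproduce and are not in dispute.

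**12-month type I error.** Inputs: 12-month SD 13% (section D.3), equal SDs in the two arms, complete data. The month-4 SD, written s, is not in the documents and is varied. The model estimates the common variance as about (s² + 13²)/2. The 12-month standard error is therefore off by the factor r = sqrt((s² + 169)/2)/13, and the true two-sided error is 2·P(Z > 1.96·r).

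| Month-4 SD s | (s² + 169)/2 | r | Two-sided error |
|---|---|---|---|
| 3% | 89.0 | 0.726 | 0.155 |
| 5% | 97.0 | 0.758 | 0.138 |
| 8% | 116.5 | 0.830 | 0.104 |
| 9.4% | 128.7 | 0.873 | 0.087 |
| 11.2% | 147.2 | 0.933 | 0.067 |
| 13% | 169.0 | 1.000 | 0.050 |
| 16% | 212.5 | 1.121 | 0.028 |

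As s goes to 0 the limit is 2·P(Z > 1.96/√2) = 0.166.

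**Which s is plausible.** If SD scales with mean loss (an assumption), the 25% loss by month 4 quoted in section C gives 25 × 3/8 = 9.4% or 25 × 13/29 = 11.2%. The 4- versus 16-month losses in section C give 13 × 25/33 = 9.8% and 13 × 24/34 = 9.2%, if the 16-month loss stands in for 12 months. These values put the error at about 0.07-0.09.

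**Simulation.** With 40,000 trials per setting, correlations of 0.3 to 0.7, REML compound symmetry and Satterthwaite df, N = 39 (26:13) gave 0.155-0.156, 0.103-0.104, 0.084-0.087, 0.065-0.069 and 0.028 at s = 3, 8, 9.4, 11.2 and 16%. N = 33 agreed within 0.01. Visit-specific variance gave 0.048-0.052. Fitted REML models with a baseline covariate (312-348 trials each) gave 0.147, 0.096, 0.083 and 0.073 at s = 3, 8, 9.4 and 11.2%.

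**Fewer scans at month 12.** Weighting by scans, the variance is (48s² + n·169)/(48 + n). With n = 39 or 33 the error is 0.18 or 0.19 at s = 3%, and 0.07 for both at s = 11%.

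**Secondary hypothesis 1 at month 12.** With equal arm SDs, a true decline of 5% and level 0.05, the one-sided error P(Z > 1.645·r) is 0.12, 0.09, 0.08 and 0.06 at s = 3, 8, 9.4 and 11.2%. In simulation it is not inflated if the ZA SD is half the placebo SD.

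**Month 4.** At N = 39, power under the stated model versus visit-specific variance is 0.03 versus 0.97 for 4 points at SD 3%. For 12.5 points it is 0.93 versus 0.97 at SD 9.4% and 0.87 versus 0.89 at SD 11.2%. For the +/-2% rule, with 26 ZA subjects and SD 13% at month 12 in both arms, the half-width cannot fall below (13/√2) × 2.0/√26 = 3.6 points, whatever s is. With its own variance the half-width is 2.0·s/√26, which is below 2 only if s is under about 5%.

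**Unequal arms (assumed ZA SD half of placebo, N = 39).** Even with visit-specific variance, pooling over arms at month 12 gives (25 × 42.25 + 12 × 169)/37 = 83.4. The model's variance of the difference is 83.4 × (1/26 + 1/13) = 9.6, against a true value of 42.25/26 + 169/13 = 14.6. The error is 2·P(Z > 1.96·sqrt(9.6/14.6)) = 0.11. Variance by visit and arm gives 0.05.

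**The case against.** The strongest reply is that the plan is under-specified, not wrong. A random intercept can be combined with visit-specific residual variances, and the text does not exclude that. This stands as a limit: the finding rests on the standard reading. But a plan that leaves the choice open allows it to be made after the data are seen, between models with materially different 12-month standard errors.

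Second, the 16% end rests on weak evidence. The 3% SD is from month 3, not month 4, in a very small study whose subjects were 22-65 days post injury, whereas this trial's baseline window is days 8-21. That is fair. The better-supported range is 0.07-0.09, and 0.16 is the extreme. SDs are given for one site only, with none for the hip, the distal femur or the ZA arm.

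Third, the fallback clause might rescue the test. Assuming a Shapiro-Wilk check at 5% and N = 39, a check pooled over visits triggers in 95% of trials at SDs 3/13. It leaves 0.055 with a Wilcoxon test at month 12 and about 0.09 with pooled ranks or log; a second simulation of pooled ranks left 0.11-0.14 at s = 3-8%. A check within visit triggers in 11% and leaves 0.15. At s = 8% the first simulation left about 0.10 under either check, and at 9.4% about 0.08. So the clause helps in one corner only. Log and logit of percent loss also fail for subjects with no loss or a gain. Secondary hypothesis 1 expects that ZA subjects "will maintain original BMD values for the hip, distal femur and proximal tibia at 4 months", which would put about half of them in that position. Log and logit are only examples, and a log of follow-up over baseline BMD is always defined, but no transformation is chosen for unequal variance.

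Fourth, the month-4 losses largely vanish at SDs of 9-11%, and there the +/-2% rule fails under either covariance structure. Both are true. The unequal-arm figures are a separate assumed case and not part of the main claim.

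**Conclusion.** The concern holds on the standard reading of the model. The 12-month proximal-tibia standard error is right only if the SDs at months 4 and 12 are equal, and the documents point to a smaller month-4 SD. Type I error is then about 0.07-0.09 at the better-supported SDs of 9-11%, rising to 0.16 at 3%. It falls below 0.05 if the month-4 SD exceeds 13%. This assumes equal arm SDs, complete data and a 12-month SD of 13%.

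That last input is itself uncertain. Section C gives 12-month proximal-tibia losses of 42% and 36% (placebo and pamidronate) for the same study from which section D.3 takes 29%. If the mean is 42% and SD scales with it, 42 × 13/29 = 18.8%, and the error is 0.11-0.12 at month-4 SDs of 11.2-9.4%.

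The mechanism is certain; its size depends on an undocumented SD. It should be fixed, with medium confidence in the magnitude.

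**What to change.** - Keep the fixed effects and replace the random intercept with an unstructured 2x2 within-subject covariance, fitted by REML with Kenward-Roger degrees of freedom. ANCOVA at each visit is an acceptable alternative.
- Take the month-4 interval and the one-sided 12-month test of secondary hypothesis 1 from the same model.
- Prespecify one sensitivity analysis with arm-specific variances, because 2:1 allocation makes pooling over arms risky if the ZA SD is smaller.
- State that any normality check is made within visit and is not the remedy for unequal variance.
- Reconcile the 29% and 42% proximal-tibia figures.

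The cost is a sentence or two in section E.2, one line of model code and one more covariance parameter (three instead of two). No extra patients, visits or data are needed.
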